7.3 Impact analysis (baseline measurement)

Considering that Salud Escolar aims at creating healthy school environments, the impact analysis will be focused on the evaluation of some individual and environmental indicators.

Study design

A quasi-experimental design with baseline and endline evaluation will be used in schools where the School Health Program will be implemented (intervention group), and in schools where the program will not be implemented (control group). Measurements will be made prior to the start of the school program (pre-intervention), and 10 months after its implementation (post-intervention).

Study hypothesis

Based on similar studies previously carried out in the school population (Carriedo *et al.*, 2013; Safdie, Jennings-Aburto and Lévesque, 2013; McKenzie, 2015), we hypothesized the following changes in the endline measurement among children exposed to Salud Escolar, in comparison with those in the comparison group (not exposed to the intervention program):

- water consumption will increase by 171 ml (Carriedo *et al.*, 2013),
- time engaged in MVPA will increase in total 10 minutes per day, with an increase of 4 minutes per day during school recess and 4 minutes per day during physical education classes (Haerens *et al.*, 2007),
- the percentage of girls/boys who consume fruits and vegetables daily in the school environment will increase by 6.7% (Safdie, Jennings-Aburto and Lévesque, 2013).

Sample size calculation

The impact analysis study will be carried out in 30 primary schools in Mexico City (Intervention group = 15; Control Group = 15). The number of schools included was defined to better identify the effect (with a small number of schools the effect of the intervention could be confused with the characteristics of the schools) (Soto-Estrada *et al.*, 2016). Other criteria considered were the short time available for data collection (no more than three months according to reports by the Ministry of Health based on their experience during the implementation of the Health in your School program), as well as the available funds.

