Table 6 presents the sample size necessary for hypotheses testing, considering a significance level of $\alpha = 0.05$, a statistical power of 80%, and a correlation of 0.2 between the basal and final measurements. Considering that the largest sample size required is the one to estimate the effect of the intervention on fruit and vegetable consumption ($n = 388$), a design effect of 2, and 20% losses to follow-up, it is estimated that a total of 980 girls and boys ($n = 490$ per intervention group) are needed.

A baseline measurement of 1000 girls and boys has been proposed. Considering the same assumptions of design effect and loss to follow-up, it was estimated that a sample size of 595 girls and boys is required for accelerometry measurements and the System for Observing Fitness Instruction Time (SOFIT).

Table 6 The sample size required to estimate expected differences

Indicator	Standard deviation	Expected difference	Sample size
Water consumption (ml/day)	631	171	384
MVPA (min/day)	40	10	248
MVPA (min/PE)	9	3.8	248
MVPA (min/recess)	12	3.9	244
Fruit and vegetable consumption (% of schoolchildren)		6.2%	388

Note. MVPA= moderate to vigorous physical activity; PE= physical education.

Schools selection

The intervention group schools will be selected randomly from the predefined list of 58 schools selected by the Ministries of Health and Education to participate in the first phase of implementation of Salud Escolar. The control group will be selected from a list of schools available in Mexico City provided by the Ministry of Education, where the program will not be implemented. Given that the selection of the 58 schools of the intervention group will not be at random, schools from the control group will be as similar as possible to those in the intervention group. Thus, it will be sought that the schools of both groups (i.e, intervention and comparison) are paired based on the following characteristics:

- Location: schools should be in the same geographical area < 5 km.
- Basic Geostatistical Area (BGA): within a similar BGA level
- Type of working day: in the same type of working day (regular, extended or full time)
- Hours: both in the morning or in the afternoon
- Size: schools from both groups will be expected to have a similar number of students and classes.

Participants

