- C+. The 89% of households at this level have one or more transport vehicles and 91% have home broadband. Around 31% of their spending goes to food and 5% to footwear and clothing, which is, similar to other levels.
- C. The 81% of the households at this level have a head of household with studies higher than primary and 73% have home broadband. Of the total expenses of this level, 35% are destined to food and 9% to education.
- C-. In the 73% of households at this level have a head of household with studies above. Of these homes 47% have home broadband, 38% of the expenses is allocated for food, and 5% is for clothing and footwear
- D+. In 62% of households at this level, the head of the household has a higher education than primary. Only 19% have home broadband, 41% of the expenses is in food and 7% to education
- D. In 56% of households the head of the household has studies until primary school, 4% has home broadband, and 46% of the expending is in food.
- E. Most households at this level (95%) have a head of household with studies not higher than primary education and only 0.1 % have home broadband. The spending at this level allocated to food is 52%) and this is the group with the lowest proportion of spending dedicated to education (5%).

Environmental indicators

The School Audit Tool developed for the International Study of Childhood Obesity, Lifestyles and the Environment (ISCOLE) will be used to measure school environment (Broyles *et al.*, 2015). This tool has been found feasible and reliable to be applied in school contexts in different countries (Broyles *et al.*, 2015). The tool will be applied in the school of intervention and comparison groups. The School Audit Tool evaluates school policies and practices related to healthy eating and physical activity and will be carried out through direct observation and questionnaires applied to the school's administrative staff.

This tool was developed based on surveys from *The school administrator survey* (Council of Chief State School Officers, no date), from the "School Health Policies

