and Practices” (SHPPS) study (Council of Chief State School Officers, no date), from the Health Behavior in School-Aged Children (HBSC) survey (Council of Chief State School Officers, no date), and from the School Health Environment Survey (SHES) (Kroeker *et al.*, 2006). The components of the School Audit Tool assessing the school's built physical environment were taken from the school audit tool of the Sport, Physical activity and Eating behavior: Environmental Determinants in Young people (SPEEDY) study showing acceptable validity and reliability (Jones *et al.*, 2010). The tool also includes items to characterize the school grounds, the aesthetics of the school, the supply of food and access to fast-food restaurants around the school, and the amount of class time spent on physical education (Appendix 16).

Data analysis.

For the baseline evaluation, a descriptive analysis of the sample is contemplated, estimating the means and standard deviations for continuous variables, as well as percentages for categorical variables. Descriptive variables will be estimated in the total sample and by study group. A consistency in the results from the research team and the characteristics of the schools reported in the School Audit Tool will be conducted, using paired t-tests for continuous variables and Chi-square tests for categorical variables. The statistical package Stata 14 will be used for data analysis which will be disaggregated by participants sex and age.

The impact of Salud Escolar will be estimated using a difference in difference analysis considering schools as clustering variables. Behaviors of interest will be the outcome variables and group allocation and time will be the independent variables. The effect of Salud Escolar will be tested by introducing an interaction term between time and group allocation.

Fieldwork

The fieldwork will be carried out by three teams of six members, three supervisors (one for each brigade) and a coordinator. In each team two members will apply accelerometry and anthropometry measurements, four will apply the beverage diary and the 24-hour recall. Each team is estimated to work within each school for approximately one week, which represent a total of 12 schools visited in a month and two and a half months for the full data collection at the baseline stage.

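### The baseline consistency check against the School Audit Tool names paired t-tests and chi-square tests, which on the plain reading do not measure agreement (minor, secondary check)

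*Combined protocol and SAP*

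**What the plan says.** The check is one sentence in section 7.3, Data analysis, between the baseline descriptive statistics and the impact model: "A consistency in the results from the research team and the characteristics of the schools reported in the School Audit Tool will be conducted", followed by "using paired t-tests for continuous variables and Chi-square tests for categorical variables". It does not list items, define the two sources, give a threshold or say what follows from the result.

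Four other statements in section 7.3 bear on it:

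- Environmental indicators: the audit tool "will be carried out through direct observation and questionnaires applied to the school's administrative staff", and "The tool will be applied in the school of intervention and comparison groups".
- Sample size calculation: the study "will be carried out in 30 primary schools in Mexico City", 15 per group.
- Schools selection: "it will be sought that the schools of both groups (i.e, intervention and comparison) are paired" on location, area level, type of school day, shift and size.
- Data analysis, on the impact model: "Behaviors of interest will be the outcome variables and group allocation and time will be the independent variables".

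Percent agreement, kappa, ICC and Bland-Altman limits are not planned anywhere in the document.

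**The concern.** The stated purpose is consistency between what the team finds and what the audit tool reports. That is a question of agreement: how close are two readings of the same school? The named tests answer other questions. The paired t-test asks whether the average difference is zero, so errors in opposite directions cancel. The chi-square test asks either whether two classifications are associated (Pearson) or whether two proportions are equal (McNemar).

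What is at stake is how the school-environment data are reported. A non-significant t-test or a significant Pearson chi-square could be presented as evidence of consistency, although neither shows it.

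**Working it through.** The plan gives no figure for this check, so there is nothing to reproduce. **Inputs:** 30 schools (section 7.3, Sample size calculation), assuming that every school has both sources. A two-sided 5% level is also assumed; the plan states 0.05 for the sample size only. All tables, means and SDs below are constructed illustrations. Tables are written both-yes / yes-no / no-yes / both-no.

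**1. Pearson chi-square, yes/no item.** Chi-square = n(ad - bc)² / (product of the four margins).

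- 11/4/4/11: 30 × (121 - 16)² / 15⁴ = 30 × 11,025 / 50,625 = 6.53, p = 0.011. Agreement is 22/30 = 73%. Chance agreement is 50%, so kappa = (0.733 - 0.5)/0.5 = +0.47.
- 4/11/11/4: 30 × (16 - 121)² / 15⁴ = 6.53, p = 0.011. Agreement is 8/30 = 27%, kappa -0.47.

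With balanced margins chi-square = 30 × kappa², so the sign is lost.

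**2. McNemar chi-square, same tables.** Only the discordant cells count: 4 against 4, and 11 against 11. Both give p = 1. The test sees equal marginal proportions and cannot separate 73% from 27% agreement.

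**3. Paired t-test, continuous item.** It is significant when |mean difference| > t(0.975, 29)/√30 × SD of differences = 2.045/5.477 = 0.373 SD. Limits of agreement are mean ± 1.96 SD.

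- Mean difference 3, SD 10: t = 1.64, p = 0.11, limits -16.6 to +22.6. Not significant, with wide disagreement.
- Mean difference 0.5, SD 1: t = 2.74, p = 0.010, limits -1.5 to +2.5. Significant, with close agreement.

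The noisier source passes more easily.

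**4. Is there an item that both sources could record?** Section 7.3, Data analysis and the text just before it, lists class time given to physical education among the audit tool's contents. Section 7.3, Direct observation, has the team record the frequency of physical education sessions and their scheduled and actual duration. This is a candidate. Whether the items measure the same quantity cannot be confirmed from the text.

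**5. The alternative reading: 15 matched pairs of schools.** Take 12/15 against 6/15 on a yes/no item. Unpaired Pearson chi-square = 30 × (12×9 - 3×6)² / (15×15×18×12) = 5.0, p = 0.025, whatever the pairing. The discordant pairs that fit these margins are 6v0, 7v1, 8v2 and 9v3, with exact McNemar p = 0.031, 0.070, 0.109 and 0.146.

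**6. Precision of agreement measures with 30 schools.**

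- Kappa 0.47: SE = √(0.733×0.267/(30×0.25)) = 0.161, 95% CI 0.15 to 0.78.
- 73% agreement: Wilson 95% CI 56% to 86%.
- ICC 0.80 (two-way consistency form, F = 1.8/0.2 = 9 on 29 and 29 df): 95% CI 0.62 to 0.90.
- Each Bland-Altman limit: ± 2.045 × √(1/30 + 1.96²/58) = ± 0.65 SD of the differences.
- Rare item, 28/1/1/0: agreement 93%, but kappa = (0.9333 - 0.9356)/(1 - 0.9356) = -0.03.

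**The case against.** The strongest reply is that the sentence is garbled and may not describe an agreement check at all. The intervention schools are not a random choice, pairing with controls is sought, the preceding sentence describes variables by study group, and the test named is a paired one. No other baseline comparison of the two groups is planned. This reading is possible. If it is right, the agreement criticism falls away and what remains is to make sure that the categorical test respects the pairing.

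Second, the plan says only chi-square, which may include McNemar. That also stands. The loss of sign in step 1 then does not apply, and under the matched reading the categorical test would already be paired. McNemar would still not measure agreement between two sources.

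Third, the paired t-test is incomplete rather than wrong, because a systematic difference is one part of agreement. This is fair, and the mean difference should be kept.

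Fourth, only the number of schools comes from the plan. The illustrations show how the tests behave, not how large any error would be in this study.

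A reader might go further and infer that the evaluation of the program's impact is compromised. The document does not support that. The difference-in-difference model uses behaviors, group and time; the audit comparison does not enter it, and no decision rule depends on the result.

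**Conclusion.** The point holds in a limited form. If the sentence means two sources describing the same school, the planned tests cannot show consistency: the t-test addresses only the mean difference, and neither type of chi-square separates agreement from disagreement in the tables above. If it means matched intervention and control schools, the plan needs only to say so and to use a paired categorical test. Under either reading the analyst would have to guess what is compared with what.

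The matter is minor. Means, SDs and percentages are planned in any case, and sample size, power and the impact estimate do not depend on this check. Confidence is medium because the sentence is ambiguous. The figures rest on 30 schools with both sources and on constructed data.

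**What to change.** Rewrite the sentence to name the items, the two sources and the unit compared. Then:

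- **Same quantity, categorical:** replace the chi-square test with percent agreement plus Cohen's kappa with 95% CI, weighted if the item is ordinal.
- **Same quantity, continuous:** replace the t-test with the mean difference, Bland-Altman limits, and an ICC with 95% CI, with the form of ICC stated in advance. Physical education class time is the first item to examine.
- **Different quantities** (for example scheduled against actual minutes): report the mean difference with CI and do not call it consistency.
- **If matched schools were meant:** say so, and use a paired test such as exact McNemar for categorical items, to go with the paired t-test.

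The cost is a change of wording and a few lines of code, with no extra fieldwork for items that both sources already record. The downside is precision: with about 30 schools the intervals are wide, and kappa is unstable for rare items, so percent agreement must stand beside it.

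### The stated 80% power does not apply to the group-by-time interaction that will be tested: on the plan's own inputs it is about 56% for water and 33% for daily MVPA

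*Combined protocol and SAP*

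**What the plan says.** The Sample size calculation in section 7.3 sets a significance level of 0.05 and "a statistical power of 80%, and a correlation of 0.2 between the basal and final measurements". It adds a design effect of 2 and 20% losses, reaching 980 children (490 per group) for the main sample and 595 for accelerometry and SOFIT. The hypothesis is that "water consumption will increase by 171 ml", and the Table 6 row (SD, difference, n) reads "Water consumption (ml/day) 631 171 384". The daily MVPA row has SD 40, difference 10 and n 248.

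The Data analysis paragraph of the same section plans a difference-in-differences analysis with schools as clusters: "Behaviors of interest will be the outcome variables and group allocation and time will be the independent variables", and "The effect of Salud Escolar will be tested by introducing an interaction term between time and group allocation". It names no term linking a child's two measurements. The sample size text does not say which formula used the 0.2, or whether it refers to children or to school means.

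**The concern.** The power claim and the test should refer to the same contrast. The interaction is a difference between two mean changes, so it carries the noise of both waves, reduced only by their correlation. At 0.2 that reduction is small. If the sample was not sized for this contrast, a true 171 ml/day gain in water, or a true 10-minute gain in MVPA, could well be reported as no demonstrated impact. Section 9 says the results are meant to inform nationwide scaling, so a falsely reassuring 80% matters when a null result is read.

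**Working it through.** **Inputs (section 7.3).** Alpha 0.05, taken as two-sided because sidedness is not stated; power 80%; correlation r = 0.2; design effect 2; losses 20%; 15 + 15 schools. Water: SD 631, difference 171, so d = 0.271. Daily MVPA: SD 40, difference 10, so d = 0.25. The SDs are read as cross-sectional and equal in both waves.

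**1. The plan's own figures.** 388 x 2 / 0.8 = 970, close to the 980 stated; 248 x 2 x 1.2 = 595.2, matching 595. Both treat a Table 6 entry as a total over the two arms, so water has 192 per arm and daily MVPA 124. The entries themselves do not come from one formula. With shared alpha, power and r, n / (SD/difference)^2 should be constant, but it is 28.2 for water, 15.5 for daily MVPA, 44.2 for PE and 25.8 for recess.

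**2. Sample needed for the interaction, before inflation.** n per arm = 2 x 2(1 - r) x (1.960 + 0.842)^2 x (SD/difference)^2.
- Water: 2 x 1.6 x 7.849 x 13.617 = 342 per arm, 684 in total (384 stated).
- Daily MVPA: 2 x 1.6 x 7.849 x 16 = 402 per arm, 804 in total (248 stated).

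**3. Power with the planned numbers.** Effective n per arm = children x 0.8 / 2 (design effect) / 2 (arms). In SD units SE = sqrt(1.6 x 2 / n), and power = Phi(d/SE - 1.960).
- Water: 980 gives n = 196; SE = 0.1278; Phi(2.121 - 1.960) = 56%.
- Daily MVPA: 595 gives n = 119; SE = 0.1640; Phi(1.525 - 1.960) = 33%.

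**4. Level of the correlation.** Let c be the correlation between waves of the school-level component, with 0.2 kept as the overall child-level correlation. A design effect of 2 means ICC x (m - 1) = 1, where m is children per school. The correlation of the compared means is then (0.2 + c)/2 and the variance factor is 1.8 - c. Step 3 is the case c = 0.2. The last column is explained in step 5.

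| c (assumed) | Factor | Water, 980 | Daily MVPA, 595 | Water, grades 3-6 only |
|---|---|---|---|---|
| 0 | 1.8 | 52% | 30% | 37% |
| 0.2 | 1.6 | 56% | 33% | 41% |
| 0.5 | 1.3 | 65% | 39% | 48% |
| 0.8 | 1.0 | 77% | 49% | 59% |
| 0.9 | 0.9 | 81% | 53% | 64% |
| 1.0 | 0.8 | 85% | 58% | 69% |

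**5. Who supplies water data.** Children are sampled from grades 1-6, but the Beverage Diary goes to grades 3-6. Assuming 4/6 of the sample, 980 x 4/6 = 653 children and n = 653 x 0.8 / 2 / 2 = 131 per arm, which gives the last column. That column keeps the design effect at 2. If instead the ICC is held at 1/(26.1 - 1) = 0.040, with 17.4 children per school, the design effect is 1 + 16.4 x 0.040 = 1.65 and n = 158. At c = 0.2, power is then Phi(0.271/0.1423 - 1.960) = 48%.

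**6. Other readings.** Starting from the proposed 1,000 children gives 57% for water, or 54% using t with 28 df. A one-sided test gives Phi(2.121 - 1.645) = 68% for water and Phi(1.525 - 1.645) = 45% for MVPA. If the Table 6 SDs were SDs of change, the factor would be 1.0 and power 77% and 49%. None of these reaches 80%.

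PE and recess MVPA are left out because SOFIT selects target students before a lesson, and the plan does not say that the same children are observed in both waves. Fruit and vegetable consumption is left out because Table 6 gives no baseline proportion.

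**The case against.** The strongest reply is that difference in differences suits this design. Programme schools are not chosen at random, and the interaction removes a stable baseline gap if trends are parallel. That stands, and it is why the model should not be replaced.

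A reader might infer that the plan throws away about 22 points of power for water, since an endline model adjusted for baseline (factor 1 - 0.04 = 0.96) gives 78% against 56%, and that the interaction is noisier than ignoring baseline altogether. The documents do not support this. The second claim fails once the school-level correlation reaches about 0.8, and the plan does not give that correlation. The comparison also sets a test that is valid under parallel trends against one that can be biased. With a slope of 0.2, adjustment removes only a fifth of a stable gap: an assumed 50 ml gap would leave about 40 ml, or 23% of the 171 ml effect.

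Nor can one conclude that Table 6 was sized for an endline comparison. Water's 384 is nearer the endline total (428) than the interaction total (684), but PE's 248 is nearer the interaction (282) than endline only (178). The intended formula is unknown.

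A reader might also take the silence on child links to mean that the waves will be analysed as unlinked, which would give 48% for water (factor 2.0). School-level cluster-robust errors are an equally natural reading and avoid that loss.

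Finally, if 384 were per arm, water would have 84% power. The stated 490 per group rules that out. Section 7 says only the first stage is presented here, but the baseline sample is set at this stage.

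**Conclusion.** The concern holds as a mismatch between the power statement and the named test. On the plan's inputs, with 0.2 applied throughout, power is about 56% for water and 33% for daily MVPA. The MVPA shortfall is robust: even a perfectly stable school-level component gives only about 58%. The water shortfall is conditional. It disappears at a school-level correlation of about 0.9 or above if all 980 children supply data, but not if only grades 3-6 do (about 69% at most, on the 4/6 assumption).

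These figures assume a two-sided test, cross-sectional SDs equal in both waves, a design effect of 2 and a normal approximation, which is slightly optimistic with 30 schools. They do not show that difference in differences is the wrong model, or that baseline adjustment would recover the lost power at no cost.

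**What to change.** 1. Keep difference in differences as the primary analysis, because schools are not randomised.
2. In the Sample size calculation, restate power for the group-by-time contrast. State sidedness, what the SDs refer to, and the level at which the 0.2 applies. Give a range for the school-level correlation between waves, and the number of children expected to supply each outcome (grades 3-6 for the diary, the subsample for accelerometry).
3. In Data analysis, state that each child's two measurements are linked, with clustering at school level, wherever the same children are measured twice. Say whether that is so for the SOFIT outcomes.
4. Optionally, for outcomes with linked measurements only, prespecify an endline model adjusted for baseline as a sensitivity analysis. State that it keeps part of any true baseline gap. It should neither replace the primary estimate nor be a condition for claiming impact.

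The cost is wording and a recalculation, plus one extra regression per outcome if item 4 is taken up; no new data are needed. The restatement recovers no power. If the restated figures are judged too low, the sponsor must either enlarge the sample or say in advance that a null result for these outcomes would be inconclusive.
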